Several decades ago, the Clinical, Etiology, Anatomic, Pathophysiology (CEAP) classification was created to standardize the diverse manifestations of chronic venous insufficiency to allow for easier classification and communication of disease severity⁹. Specifically, within the Clinical portion of the CEAP system, the subcomponents C3-C5 refer to edema (C3), changes in skin and subcutaneous tissue (C4 -pigmentation, dermatitis, lipodermatosclerosis or atrophie blanche), and a healed ulcer (C5); these subcomponents increase numerically in proportion to the severity of the patient's condition¹⁰.

Currently, compression therapy is the first line treatment for all the manifestations of CVI ¹¹. However, existing compression hosiery are met with resistance by some patients. This results in a gap in compliance as for example up to 80% of patients who are prescribed compression stockings or bandaging wraps do not wear them as prescribed¹². This practice gap may contribute to the overall burden of CVI and solutions that address the need of patients who cannot wear compression stockings are needed. Inelastic compression wraps may help to solve this practice gap by offering easier application without compromising outcomes. One example of such a system is the Compreflex Compression Wrap system (Sigvaris Inc. Peachtree City, GA). This proposal is focused

Page 2 of 12

PI: [name]

Date: 07Sep2022 Version: 2.0

on determining if the usage of this specific inelastic compression wrap system in patients with CVI stages C3, C4, and C5 improves their quality of life.

4) Inclusion and Exclusion Criteria

Inclusion Criteria

- Subject is age 18 or older, able and willing to provide consent and agrees to comply with the study procedures
- Subject must have chronic venous insufficiency of stages C3, C4, or C5 according to the CEAP classification system
- Not compliant with their currently prescribed compression system

Exclusion Criteria

- Active malignancy other than non-melanoma skin cancer
- Study ulcer suspicious for cancer
- Unable to provide consent
- Subjects who are pregnant and/or breastfeeding
- In the opinion of the PI the subject cannot comply with study procedures

5) Study Design

- a) Primary Purpose: Treatment
- b) Interventional Study Model: Single Group
- c) Allocation: N/Ad) Enrollment: 40

This is a single center, single intervention, unblinded, prospective cohort study.

6)

7) Procedures Involved

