This is a single center prospective cohort study that will last up to six 6 weeks per subject. A total of 30 patients will be enrolled, through the University of Miami Hospital and Clinics. The study is comprised of 3 visits per subject (see table 1) two in person and one over the phone. V0 will occur on the first day of the study. V1 will occur during the second week (between days 714) and the final visit, V2 on day 42 of the study.

At the enrollment visit (V0), subjects will undergo baseline assessments to determine eligibility for the study (inclusion and exclusion criteria, demographics, medical history, medication history, focused physical exam). Medical records will be reviewed for the subject's basic demographics, medical and surgical history, and current treatments. Once eligibility is confirmed, the patient will be assessed for measurements of disease severity (presence of varicose veins, atrophe

PI: [name]

Date: 07Sep2022 Version: 2.0

blanche, lipodermatosclerosis, hyperpigmentation, the Venous Clinical Severity Score VCSS (See Appendix A), itch severity using itch Numerical Rating Scale NRS (See Appendix B), pain using the Visual Analogue Scale VAS (See Appendix C), and limb circumference in mm.) Upon proper consent, photographs of the extremity will be captured and quality of life assessments will be completed. The two quality of life assessments used will be the Chronic Venous Disease Quality of Life Questionnaire (CIVIQ – 20) (See Appendix D), and the Short Form Healthy Survey (SF-36) (See Appendix E). The initial visit will conclude with proper product application training and time to address any questions.

Subjects will report for 2 successive follow-up visits. The first follow-up visit will be completed at least one week but no later than 14 days after the initial visit and be completed via phone (V1). During this visit, study staff will document concomitant medications, itch severity, pain, and assess patient adherence to usage of the inelastic compression system. If in the opinion of the study staff the subject is not able to apply the ICS effectively, they may convert the visit to video conferencing or even in person visit.

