The third and final visit (V2) will be completed in person at the University of Miami Hospital Dermatology Clinical Trials Unit 6 weeks after the initial in person visit. During this visit, similar to the initial visit, study staff will document concomitant medications, perform a focused exam, measure disease severity and itch severity, and assess pain. Additionally, limb circumference measurements will be obtained and photographs of the extremity will be captured again. The visit will conclude with the same two quality of life assessments and assessment of adherence.

All subjects will continue to follow their care for all medical conditions as prescribed by their physician.

Visit	V0	V1 (phone)	V2
Day	0	7-14	42 (+/- 3)
Informed consent	X		
Eligibility	X		
Medical history	X		
Concomitant medications	X	X	X
Focused exam	X		X
Disease severity assessments	X		X
Itch severity	X	X	X
Pain assessment	X	X	X
Limb circumference	X		X
Photography	X		X
QOL assessment (CIVIQ-20, SF 36)	X		X
Product application training	X		
Adherence assessment		X	X

PI: [name]

Date: 07Sep2022 Version: 2.0

8) Study Endpoint

a) Primary Outcome Measure

- i) Title: Change in the Quality of Life
- ii) Description: As measured by the Chronic Venous Disease Quality of Life Questionnaire (CIVIQ-20) which is a questionnaire made up of 20 multiple choice questions subdivided into four categories: psychology, pain, physical repercussion and social repercussions. The questions are equally weighted and the value indicates the degree of deterioration of quality of life; 0 being the highest quality of life and 100 being the lowest. It has been tested to be a reliable measurement tool in evaluating the quality of life in those with CVI.
- iii) Timeframe: Baseline to 6 weeks

9) Data Banking

Physical study records will be in a locked cabinet in the Dermatology Clinical Trials Unit at University of Miami (University of Miami Hospital West Building, [name]). Technological study records will be located on a spreadsheet within a project file located within a password protected server on Microsoft Teams.

10) Data Management

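### At the final visit the self-reported primary outcome is completed after unblinded staff have examined, measured and photographed the leg, which leaves room for an avoidable cue about change

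*Protocol*

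**What the plan says.** Section 7 of the protocol (Procedures Involved) describes V2 in sequence. First, "study staff will document concomitant medications, perform a focused exam, measure disease severity and itch severity, and assess pain". Next, "Additionally, limb circumference measurements will be obtained and photographs of the extremity will be captured again". Then: "The visit will conclude with the same two quality of life assessments and assessment of adherence". The two quality-of-life instruments are the CIVIQ-20 and the SF-36.

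At V0 the same section puts severity scoring, itch, pain and circumference first and goes on: "photographs of the extremity will be captured and quality of life assessments will be completed". Product training ends that visit. The focused physical exam at V0 is one of the assessments used to establish eligibility.

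Section 8 makes the CIVIQ-20 the primary outcome, with "Timeframe: Baseline to 6 weeks". Section 5 describes the design: "This is a single center, single intervention, unblinded, prospective cohort study". The model is a single group.

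The visit table also lists quality of life below the exam, severity, circumference and photography rows, but a table of this kind does not set an order. The point rests on the narrative text.

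**The concern.** The CIVIQ-20 is the subject's own report, and the V2 score enters the primary change score directly. Under the Section 7 order, the subject answers it after staff who know the treatment have repeated the circumference, severity scoring and photographs. These procedures can show whether the leg has changed. Section 13 names less swelling and less discoloration as benefits that subjects can reasonably expect, and these are among the features the V2 procedures can reveal.

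If a subject hears or senses at that moment that the leg is better, the answers may move for a reason other than six weeks of lived experience. Such a shift would be read as a change in quality of life with the compression system. An analysis plan cannot undo the order in which the data were collected, so the remedy belongs in the protocol.

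**Working it through.** The documents give no figure to reproduce on this point. The check is a comparison of the two visits, followed by an illustration of scale.

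**Order at the two visits (Section 7)**

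| Step | V0 | V2 |
|---|---|---|
| Focused exam | before QOL (part of eligibility) | before QOL |
| Severity, itch, pain | before QOL | before QOL |
| Limb circumference | before QOL | before QOL |
| Photographs | before QOL | before QOL |
| Product training | after QOL | not done |
| Adherence assessment | not done | same closing block as QOL |
| Earlier study measurement to compare with | none | V0 values and photographs |

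**What cancels.** Write the reported score as true score + a + c. Here a is a constant effect of having just been examined and asked about pain and itch, and c is an effect of a cue about change since baseline.

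- V0 score = true(0) + a, because no earlier study measurement exists and so c = 0.
- V2 score = true(6) + a + c.
- V2 − V0 = [true(6) − true(0)] + c.

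The constant part drops out so far as it really is the same at both visits. The cue about change stays in full. It can have either sign: a leg seen as unchanged or worse gives no cue or an opposite one.

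**Illustration of scale (all sizes assumed).** The protocol states no SD, test or alpha. Assume a two-sided 5% paired t-test, zero true change, and an average shift b in units of the SD of the 6-week change. With noncentrality δ = b√n and critical value t* = t(0.975, n−1), where F is the noncentral t distribution function with n−1 degrees of freedom:

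P(nominally significant) = 1 − F(t*; δ) + F(−t*; δ)

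Both sample sizes are shown because Section 5 gives 40 and Section 7 gives 30.

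| b (assumed) | δ, n=30 | P, n=30 | δ, n=40 | P, n=40 |
|---|---|---|---|---|
| 0 | 0 | 5.0% | 0 | 5.0% |
| 0.1 SD | 0.548 | 8.3% | 0.632 | 9.5% |
| 0.2 SD | 1.095 | 18.5% | 1.265 | 23.5% |
| 0.3 SD | 1.643 | 35.5% | 1.897 | 45.7% |

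For comparison, the 95% confidence interval half-width is t*/√n, which is 0.373 SD at n=30 and 0.320 SD at n=40. A shift of 0.1 SD is well inside that width, so the data would not reveal it.

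**The case against.** **Feedback is not documented.** A reader might infer that staff tell subjects their leg has improved before the forms are completed. No section says so. The protocol only leaves the possibility open. This stands, and the point is a risk, not an observed bias.

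**V0 has a similar order.** This removes a constant effect of being examined first, including the overlap between the pain rating and the CIVIQ-20 pain category. It does not remove a cue about change, which needs a baseline and so can occur only at V2.

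**Subjects already know.** They use the system for six weeks, know they are treated, and can see and feel changes in swelling. The open-label reporting bias exists whatever the order of the forms, and the added same-day cue may be small. This stands, and it limits the weight of the point.

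**The percentages are generic.** A reader might take them as the trial's false-positive rate. They are not: the shift and the test are assumed, and any bias of the same size from any source would give the same figures.

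**A control arm would not simply absorb the cue.** One might infer that the single-group design is what makes the order harmful. In an open randomised trial, feedback about improvement would itself differ by arm. The lack of a control is a separate and larger matter and lends no weight here.

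**A simple reordering can clash with eligibility.** Placing the forms after eligibility but before the focused exam is impossible at V0, because that exam is part of eligibility. Placing them after the exam at V0 and before it at V2 would unmatch the two visits. This stands and shapes the fix.

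**Conclusion.** The point holds as a minor-to-moderate weakness in the visit procedure. Section 7 puts the primary questionnaire in the closing block of V2, after unblinded examination, measurement and photography. Any cue about change since baseline would enter the primary change score and would not be offset by the similar order at V0.

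The size is unknown. The illustrative rates rest on an assumed shift and an assumed test, and show only that a shift too small to notice would matter somewhat at n=30 or n=40.

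The documents do not support saying that feedback is given, that the result is biased in a known direction, or that the CIVIQ-20 is strictly the last item: it shares the closing block with the SF-36 and the adherence assessment, and the order within that block is not clearly fixed. Reordering would reduce an avoidable addition to the reporting bias. The open-label part would remain.

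**What to change.** In Section 7, state that at both V0 and V2 subjects self-complete the CIVIQ-20 and then the SF-36 at the same point in the visit:

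- V0: right after informed consent, before the focused exam that forms part of eligibility.
- V2: on arrival.

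At both visits this comes before the exam, severity, itch and pain ratings, circumference and photography. It also comes before product training at V0 and the adherence assessment at V2. Add that staff do not discuss findings with the subject until the forms are handed in. The sentence that closes the V2 description, and the V0 text that places the questionnaires after the photographs, need rewording to match.

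The cost is a few sentences and a reordered visit checklist, with no new procedure. A few people who then prove ineligible at V0 will have filled in the forms. The documents do not show whether any subject has already completed V0 under the present order. If some have, the order used at each visit should be recorded, so that subjects with unmatched visits can be identified.

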Medical and scientific judgment should be exercised in determining whether an event is an important medical event. An important medical event may not be immediately lifethreatening and/or result in death or hospitalization. However, the important medical event should be reported as serious, if it is determined that the event may jeopardize the Participant and/or may require intervention to prevent one of the other adverse event outcomes.

CLASSIFICATION OF AN ADVERSE EVENT SEVERITY OF EVENT

The Investigator will provide an assessment of the severity of each adverse reaction by recording a severity rating on the appropriate SAE reporting page of the Participant's file. Severity, which is a description of the intensity of manifestation of the SAE, is distinct from seriousness, which implies a patient outcome or SAE-required treatment measure associated with a threat to life or functionality. Severity will be assessed according to the following scale. If required on the adverse event case report forms, the investigator will use the adjectives MILD, MODERATE, or SEVERE to describe the maximum intensity of the adverse event. For purposes of consistency, these intensity grades are defined as follows:

Page 6 of 12 Revised: June 17, 2020

PI: [name]

Date: 07Sep2022 Version: 2.0

MILD Does not interfere with Participant's usual

function.

MODERATE Interferes to some extent with Participant's

usual function.

SEVERE Interferes significantly with Participant's

usual function.

RELATIONSHIP TO STUDY INTERVENTION

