For all collected AEs, the clinician who examines and evaluates the participant will determine the AE's causality based on temporal relationship and his/her clinical judgment. A binary assessment (related/not related) will be made and take into consideration the natural history of the underlying disease, concurrent illness, concomitant therapy, study-related procedures, accidents, and other external factors. While the relationship to the study tissue biopsy procedure (study research intervention) (related/not related) is part of the documentation process, it is not a factor in determining what is or is not reported in the study. All AEs are recorded regardless of relatedness. Related: The AE is known to occur with the study research procedure, there is a reasonable possibility that the study research procedure caused the AE, or there is a temporal relationship between the study agent and event. Reasonable possibility means that there is evidence to suggest a causal relationship between the study research procedure and the AE. An AE can be deemed related even if other factors may have contributed to the event.

Not Related: There is not a reasonable possibility that the study research procedure caused the event, there is no temporal relationship between the study research procedure and event onset, or an alternate etiology has been established or appears to provide a plausible explanation (e.g. the participant's clinical condition, underlying disease or concomitant treatments).

TIME PERIOD AND FREQUENCY FOR EVENT ASSESSMENT AND FOLLOW-UP At each visit, AEs/SAEs will be evaluated by the Investigator and recorded. All AEs must be recorded irrespective of whether they are considered study related. Information to be collected includes event description, time of onset, clinician's assessment of severity, relationship to study procedures, and time of resolution/stabilization of the event. All AEs occurring while on study must be documented appropriately regardless of relationship.

Any medical condition that is present at the time that the participant is screened will be considered as baseline and not reported as an AE.

Changes in the severity of an AE will be documented to allow an assessment of the duration of the event at each level of severity to be performed.

PI: [name]

Date: 07Sep2022 Version: 2.0

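### Section 12 judges adverse-event relatedness against a tissue biopsy the trial does not perform, never names the compression wrap, and lets one event be both Related and Not Related

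*Protocol*

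**What the plan says.** The relevant text is the part of Protocol Section 12 headed "RELATIONSHIP TO STUDY INTERVENTION". It asks the examining clinician for a binary judgement, and then says: "While the relationship to the study tissue biopsy procedure (study research intervention) (related/not related) is part of the documentation process". The same sentence adds that this judgement does not decide what gets reported.

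Two definitions follow, each a list of alternatives joined by 'or'.

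- **Related** is met, among other ways, if "there is a temporal relationship between the study agent and event". A further sentence says: "An AE can be deemed related even if other factors may have contributed to the event".
- **Not Related** is met, among other ways, if "there is no temporal relationship between the study research procedure and event onset", or if "an alternate etiology has been established or appears to provide a plausible explanation". The underlying disease is one of the examples given for that last alternative.

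The list of AE data items uses yet another term: "relationship to study procedures, and time of resolution/stabilization of the event". The AE definition at the start of Section 12 equates an intervention with a study research procedure and does not say what that covers.

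Under serious adverse event (SAE) reporting, the main sentence sets a 24-hour IRB notice for SAEs related to the study research procedures.

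**The concern.** A relatedness rule needs a stated exposure and two categories that exclude each other. Section 12 provides neither. The one parenthesis that says what the research intervention is points to a biopsy, and the compression wrap is not mentioned. Separately, the two definitions can both be satisfied by the same event, although the assessment is meant to be binary.

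At stake is how wrap events are classified. The trial has one group, so there is no control rate against which to check a clinician's attribution. In addition, the main 24-hour IRB notice for SAEs turns on this label.

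**Working it through.** The protocol gives no figure on this point to reproduce. The check sets the texts side by side.

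**1. Is there a biopsy?** Section 7 and its visit table list 13 items, from informed consent to adherence assessment. None is a biopsy at V0, V1 or V2. Section 11 lists four risks, all attributed to the compression system. Section 5 describes a single-intervention study, and Section 3 identifies that intervention as the wrap.

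**2. Does Section 12 name the wrap?** No. The words compression, ICS, wrap and device each occur 0 times in Section 12. The terms used instead are:

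| Term in Section 12 | Occurrences |
|---|---|
| study research procedure(s) | 7 |
| study agent | 1 |
| study procedures | 1 |
| study-related procedures | 1 |
| study tissue biopsy procedure | 1 |

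None is defined so as to include the wrap.

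**3. Do the two timing criteria use the same reference?** No.

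| Category | Timing criterion |
|---|---|
| Related | "there is a temporal relationship between the study agent and event" |
| Not Related | "there is no temporal relationship between the study research procedure and event onset" |

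If the agent is taken to be the wrap and the procedures to be the visit assessments, pain that follows wrapping but no visit procedure meets both criteria.

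**4. Does a common reference cure this?** It removes the conflict in step 3 but not the overlap. Suppose every term means the wrap, and a subject with C4 disease develops new skin irritation while wearing it.

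- Timing alone makes the event Related.
- Venous disease is a plausible other explanation, so under "an alternate etiology has been established or appears to provide a plausible explanation" the event is Not Related.

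No sentence says which category prevails.

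**5. Which listed risks are exposed to that overlap?** Section 11 lists skin irritation or discomfort, pain, soft tissue injury and nerve injury. Section 3 attributes dermatitis (C4) and pain to the disease itself, and every subject has C3 to C5 disease by inclusion. So 2 of the 4 risks resemble the disease. Conditions present at screening count as baseline and are not AEs, so the overlap concerns new events only.

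**6. Where does the label change anything?**

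- Recording: no effect. All AEs are recorded whatever the judged cause.
- Reporting to the IRB: no effect on whether an AE is reported. That sentence states no deadline.
- Counting as serious: no effect. The SAE definition applies whatever the judged cause.
- Main 24-hour notice: depends on relatedness.

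Section 12 lists 6 seriousness criteria and adds one for which "the important medical event should be reported as serious", so 6 + 1 = 7 routes. Death and life-threatening events have an immediate-notice sentence: 7 − 2 = 5. Congenital anomaly can be set aside, since pregnancy is excluded and follow-up is six weeks: 5 − 1 = 4. These four are hospitalization, disability or incapacity, intervention to prevent permanent impairment, and the important medical event. For them the label can affect the speed of notice, except where the investigator learns of the event late. The delayed-awareness sentence also sets 24 hours and states no relatedness condition.

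**The case against.** The strongest reply is that a clinician has only one candidate intervention. The biopsy phrase occurs once, its parenthesis glosses it as the research intervention, the heading above it refers to the study intervention, and the preceding section is about the risks of the compression system. Section 13 speaks of using the system as part of the study. The definitions are also not meant for mechanical matching: Section 12 asks for clinical judgement that weighs timing, underlying disease and other therapy. It states that "An AE can be deemed related even if other factors may have contributed to the event", which addresses the mixed-cause case.

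Much of this stands. Most clinicians would probably look to the wrap, and judgement would settle many cases. It does not repair the text. The contributing-factors sentence is permissive and gives Related no precedence over a plausible alternative cause, so two careful clinicians could label the same event differently and both be within the protocol. Section 13 is also mixed, since it describes the study as mirroring standard care.

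Three stronger readings are tempting, and the protocol does not support them.

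- **Wrap injuries would go unrecorded or unreported.** All AEs are recorded and go to the IRB.
- **The label is unreliable for every wrap injury.** The protocol describes no disease look-alike for soft tissue or nerve injury. These are exposed only to the undefined reference, which context partly resolves.
- **Counting the overlapping combinations of criteria measures the harm.** Such a count depends on which criteria are treated as independent, and it says nothing about how many events are affected.

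**Conclusion.** The point holds in limited form. As written, Section 12 documents relatedness against a procedure that no subject undergoes, omits the trial's single intervention, uses different references in its two timing criteria, and lets one event satisfy both categories.

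The effect is confined to two things: the related/not related label for wrap events, chiefly new skin irritation and new pain, and possibly the speed of IRB notice for some SAEs that are neither fatal nor life-threatening. The only stated endpoint, the change in CIVIQ-20, is untouched.

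This rests on two readings. The 'or' lists are taken literally. The immediate-notice sentence for fatal or life-threatening SAEs is taken to stand on its own, although it follows the sentence about related SAEs. Section 12 also refers to local regulations, whose timelines are not shown and may shorten any delay. This is an operative safety rule that is wrong on its face and cheap to correct, so it should be amended.

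**What to change.** 1. Delete the biopsy wording.
2. Define one relatedness reference that includes the inelastic compression system, its application and the other study procedures.
3. Use that reference in the AE definition, the Related and Not Related definitions, the AE data items and the 24-hour SAE sentence, in place of the present mix of terms.
4. Make the categories mutually exclusive, for example by stating that Not Related applies only when no Related criterion is met. Steps 1 to 3 alone would leave the overlap in place.

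The cost is a wording amendment and a label change on the AE form. It adds no procedures, visits or patients.

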Any AEs/SAEs already documented at a previous assessment and designated as ongoing, should be reviewed at subsequent visits as necessary. If these have resolved, this should be documented.

ADVERSE EVENT REPORTING

All adverse events should be tracked from the time the Participant provides informed consent, and through the time of discharge from the study. Adverse events (serious and non-serious) should be recorded in the CRF for the duration of the reporting period. Adverse events reporting, including suspected serious unexpected adverse reactions, will be carried out in accordance with applicable local regulations.

All AEs that occur during the study will be recorded in the case report form and reported to IRB.

SERIOUS ADVERSE EVENT REPORTING

If a serious adverse event related to the study research procedures occurs, the IRB should be notified within 24 hours of awareness of the event by the investigator. In particular, if the serious adverse event is fatal or life-threatening, notification to IRB must be made immediately, irrespective of the extent of available adverse event information. This timeframe also applies to additional new information (follow-up) on previously forwarded serious adverse event reports.

In the rare event that the investigator does not become aware of the occurrence of a serious adverse event immediately (e.g., if an outpatient study Participant initially seeks treatment elsewhere), the investigator is to report the event within 24 hours after learning of it and document the time of his/her first awareness of the adverse event.

13) Potential Benefits to Subjects

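### The baseline rule in Section 12 makes no exception for worsening, so non-serious aggravation of an existing leg symptom may go unrecorded or be recorded inconsistently

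*Protocol*

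**What the plan says.** The rule is in Protocol Section 12, under the time period and frequency for event assessment. A medical condition "present at the time that the participant is screened will be considered as baseline and not reported as an AE". It carries no qualification.

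Other parts of Section 12 bear on how it is read:

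- The AE definition is broad. It takes in any unfavourable medical happening associated with the intervention, whether or not it is thought to be caused by it.
- The recording duty is also broad: "All AEs occurring while on study must be documented appropriately regardless of relationship".
- The causality assessment must "take into consideration the natural history of the underlying disease, concurrent illness, concomitant therapy". The definition of a not-related event accepts as an alternative explanation the participant's "clinical condition, underlying disease or concomitant treatments".
- On change over time: "Changes in the severity of an AE will be documented". On follow-up, the text covers "Any AEs/SAEs already documented at a previous assessment and designated as ongoing".
- On reporting: "All AEs that occur during the study will be recorded in the case report form and reported to IRB".

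Section 4 requires every subject to have CEAP stage C3, C4 or C5 disease. Section 11 lists two minor device risks (skin irritation or discomfort, and pain) and two major ones (soft tissue injury and nerve injury). It calls all of them unlikely and the minor ones likelier than the major ones.

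**The concern.** The study enrols people who already have leg disease and fits a device whose likelier harms are leg symptoms. Section 3 links venous insufficiency to pain, and stage C4 to skin changes that include dermatitis. A subject may therefore already have at screening the kind of symptom the wrap could aggravate.

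Read literally, the baseline rule removes that symptom from AE reporting for good, including when it gets worse. Read inclusively, it removes only the state at entry, and later worsening is an AE. The protocol does not choose between these readings. The same clinical course could be entered as an AE and sent to the IRB in one subject and left out in another. The not-recorded events could include ones that would count as related, because Section 12 accepts a temporal relationship as grounds for that classification.

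**Working it through.** The protocol gives no figure on this point, so the check is a reading of all of Section 12 against Sections 3, 4, 7 and 11.

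**Step 1: does any clause supply the missing exception?**

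| Text in Section 12 | What it reaches | Covers worsening of a baseline condition? |
|---|---|---|
| AE definition | Unfavourable medical happenings in general | Possibly, but not expressly |
| Duty to document all AEs on study | Events that count as AEs | Only if the worsening already counts as one |
| Severity-change sentence, directly after the baseline rule | Changes in an AE | No: the rule before it says a baseline condition is not reported as an AE |
| Follow-up of ongoing events | AEs and SAEs already documented | No |
| SAE definition and important medical events | Serious events | Yes, but only if serious |

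No clause states that worsening of a baseline condition is an AE.

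**Step 2: does other text point the other way?** It does. Weighing the natural history of the underlying disease, and naming underlying disease as a reason to call an event not related, both presuppose that events linked to existing disease are collected first and classified afterwards. The two readings therefore rest on different sentences of the same section.

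**Step 3: scope, counted from the document.**

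- Subjects with venous disease at entry: all of them, by the Section 4 criterion. That is 30 of 30 using the enrolment in Section 7, or 40 of 40 using the enrolment in Section 5.
- Device risks in Section 11: 2 minor + 2 major = 4. Those that overlap with symptoms that may already be present: 2 of 4, both minor.
- Data required for each AE. The list opens: "Information to be collected includes event description, time of onset". It goes on to severity, relationship and resolution, so 1 + 1 + 1 + 1 + 1 = 5 items.

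**Step 4: range of the effect.** Let m be the number of non-serious aggravations of conditions present at screening. The inclusive reading omits 0 events. The literal reading omits m events and 5 × m data items, together with m reports to the IRB. The document gives neither the frequency of baseline symptoms nor a rate of worsening, so m cannot be computed.

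**Step 5: what remains observable.** The visit table scores pain and itch at V0, V1 and V2. Disease severity, limb circumference, photographs and the focused exam are taken at V0 and V2. Worsening may show there, but these are outcome measurements, without onset, relatedness, resolution or IRB reporting. The table has no AE row, so the wording of Section 12 is what guides staff.

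**The case against.** The best defence is that the inclusive reading is the natural one. A baseline is a reference state against which change is judged. An aggravation after entry is an unfavourable medical happening, AEs are tracked from consent to discharge, and the causality text would have little to do for the disease every subject has if that disease could never produce an AE. On this view the protocol lacks only a clarifying clause. The practical exposure is also narrow:

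- C3 to C5 disease does not mean that every subject has pain or irritated skin at screening.
- New symptoms are AEs on either reading, and serious worsening is covered.
- The device risks are called unlikely.
- This is a single-centre, six-week study in which pain and itch are scored at all three visits.

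The points on exposure stand and limit the size of the concern. The point on interpretation stands only in part. The inclusive reading is reasonable, but the text does not settle it, and the sentence most directly on the subject says not to report the condition. What counts as an AE is a collection rule that this protocol has itself fixed, so it cannot be left to the analysis stage. The symptom scores reduce the loss of signal but do not replace the AE record.

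It can also be objected that Section 12 ties relatedness to a tissue biopsy procedure that appears nowhere in the study procedures, so relatedness to the wrap would remain unclear even after the fix. That is a separate defect that needs its own correction. It does not make this fix unsound.

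**Conclusion.** The concern holds. Section 12 states an exclusion that, followed literally, drops non-serious worsening of conditions present at screening from AE recording and IRB reporting, while other text in the section implies that such events are collected. The rule touches every subject, and it overlaps with the two likelier device risks.

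The number of events affected is unknown, from none to all non-serious aggravations, depending on how staff read the rule. The conclusion assumes only that some subjects enter with leg symptoms that could worsen, which the protocol's account of the disease makes plausible but does not quantify. The effect is confined to the completeness and consistency of the safety record. New symptoms, serious events and the CIVIQ-20 primary endpoint are not affected. The wording should be changed; the gap does not undermine the main analysis.

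**What to change.** Reconcile the passages by adding one sentence directly after the baseline rule in Section 12, for example:

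> If, in the investigator's judgement, such a condition worsens after V0 beyond its baseline state, the worsening is recorded as an AE with onset at the time of worsening, graded on the existing mild/moderate/severe scale and assessed for relatedness.

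Because this rests on clinical judgement, a small change in a pain or itch score does not by itself become an AE.

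The cost is one sentence and no new assessments. A few more AEs may be recorded and reported to the IRB, so the safety listing may look slightly less favourable.
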